Research Protocol (revised July 7, 2014)

Project Title: Mammographic Density and Soy Isoflavones

Principal Investigator: [name].

Dept of Preventive Medicine and Community Health
University of Texas Medical Branch, [name]
[contact]
[contact]
[contact]

Abstract. Populations consuming high levels of soy, as in many Asian countries, have lower levels of ovarian hormones, lower rates of breast cancer, and reduced mammographic density than populations consuming typical Western diets. These observations may in part be explained by our clinical studies that found ovarian hormone levels of premenopausal women to be lowest while they were consuming a diet that provided 15% energy from soymilk containing weakly estrogenic isoflavones. No adverse effects were observed. Further questions are whether isoflavones are the critical components influencing breast cancer risk and whether they do so by affecting other reversible risk markers for breast cancer, such as breast density. Women with dense breasts have a 4-6 fold excess risk of developing breast cancer. Moreover, greater breast density makes it more difficult to detect early breast cancer by mammography. To test the hypothesis that consumption of soy isoflavones reduces breast density, we propose a randomized, double-blind study, with two arms, and 100 premenopausal women in each arm. Women will be recruited and randomly allocated to take soy isoflavone pills (treatment) or placebo pills containing no isoflavones (control) for 2 years. The daily dose will be 120 mg of total isoflavones. Both treatment and placebo pills will contain multi-vitamin and minerals. Women will provide blood and urine samples before and during the supplement intervention period for the analyses of ovarian hormones and isoflavones. At baseline and after the intervention period, subjects will be examined for breast density by mammography and magnetic resonance imaging. The efficacy of the intervention will be determined by comparing mean changes of dense breast tissue over the 2-year intervention period in the two groups with adjustment for baseline values and individual patient characteristics of interest. We hypothesize that 1 to 2 years of a soy isoflavone supplement in premenopausal women will reduce the effects of endogenous estrogens and reduce progesterone levels further, which will explain a corresponding decrease in breast density. Our research results will have significant implications for breast cancer risk reduction. Reducing breast density can be expected to reduce the volume of target tissue at risk for breast cancer development and will improve the sensitivity of mammography for screening. The study may lead to a novel, non-invasive and economical approach to breast cancer prevention.

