If more than 6% of subjects (12 subjects) develop amenorrhea, we will break the code for these women. A transvaginal probe ultrasonography and an endometrial biopsy will be performed if amenorrhea occurs. If amenorrhea is related to soy isoflavone treatment, the study will be terminated. If this occurs, a statistically significant change in breast density is then expected because the progesterone levels of these women will be <1 ng/ml. The mammography, MRI and bone density measurements will be performed at yearly intervals and whenever subjects notify us of their intent to leave the study.

Statistical Analysis. The primary outcome variables are measures of breast density (mammographic density and relative volumes of parenchymal and adipose tissues by MRI). The main analysis will assess changes in breast density (BD) parameters over the 2-year follow-up period, measured at baseline, at one year and at two years. The efficacy analysis for the measures of BD will be analyzed primarily through mixed models for continuous outcome measures. This class of linear models can accommodate missing data and allows inclusion of time-dependent covariates for outcomes that are approximately normally distributed. Software is widely available (e.g., MIXED procedure in SAS®). We will model the marginal responses of the breast density parameters for each intervention group. The main effects of time, supplement group, and the (time x supplement group) interaction will be assessed. Time-dependent covariates (e.g., BMI) and time-independent variables (e.g., parity, age of menarche, race/ethnicity), including potential confounding variables, can be added to the models. The analysis will proceed with an intent-to-treat principle in which any subject randomized to a treatment group (i.e., placebo or soy isoflavones) with at least one post-baseline BD measure will be included in the statistical analyses. Some analyses will be conducted which will include only those patients with complete data up to a designated data collection time point (e.g., 12 months, 24 months, etc).

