Power analysis and sample size justification. The main assessment of outcome is the change from baseline in percent dense tissue. The hypothesized mean change in area of dense tissue in the soy isoflavone group will be a decrease between 10 and 15 percentage points on average, while the placebo group will remain about the same (6; 10-15). Using a two group t-test with a 0.05 two-sided significance level, and estimates of the SDs that range from 20 to 10, we will have 80% power to detect changes in mean percent of dense tissue of -10% to -20%. If we experience a 20 to 30% dropout rate, the study can still detect changes of -10% if $SD \leq 20$, and -15% or larger for $SD \leq 25$. Our choice of 100 patients per arm is robust to any violations of our assumptions, for example unanticipated study variation or higher dropout rates than expected. Additionally, we can expect the study to have even greater power than we estimate since the proposed analyses (ANCOVA, mixed models) exhibit greater power characteristics than the t-tests upon which our power analysis is based. With an estimated attrition rate of 15% over the length of the study, 100 subjects per arm should provide 85 evaluable subjects at the completion of the study. We will recruit until 200 women complete at least 1.5 years of supplement.

Results expected. Increasing the duration of consumption of soy isoflavones is expected to decrease circulating (and nipple fluid) ovarian steroids, mammographic

density, and volume of breast with parenchymal tissue relative to adipose tissue. We expect the rates of these decreases to be greater in the isoflavone group than in the placebo group. Proliferation markers in nipple aspirates and the presence of hyperplastic epithelial cells in nipple aspirates may indicate the degree of stimulatory effects of isoflavones on breast tissues. This study will show whether breast MRI which measures 3-D features of the breasts may be more sensitive in detecting breast density changes than mammography, which is a 2-D assessment. Ability to use MRI (no radiation exposure) to measure breast density will allow us to assess in the future whether soy pill supplementation intervention on breast density and breast cancer prevention may be more effective if initiated during puberty than during adulthood, as data from animal studies have shown. The effect of isoflavones on bone is hard to predict and will be examined in this study.

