Study Population: Subjects must be 30-40 years of age and be free of mammographic abnormalities. They must be willing and able to return to Galveston for scheduled study visits. We expect to enroll the 200 subjects required for the study within 6-8 months. Women will be excluded from the study if they are on contraceptive agents, any other exogenous hormones, or medications known to affect mammographic density; are pregnant or lactating; or have a previous history of cancer, breast augmentation or reduction, abnormal mammograms, or are at high risk for breast cancer (first degree relative with breast cancer). Women who are on any medically prescribed diet, or are not willing to be randomized will be excluded. Women with pacemakers or other permanent metal implants such as IUD will be excluded from the study. During initial screening, past history of allergic reactions to foods will be acquired. If subjects have prior histories of food allergies to soy food, they will be excluded. Subjects must have regular cycles and mid-luteal phase progesterone > 8 ng/ml. Perimenopausal women with > 100 pg/ml of serum estradiol on cycle day 2 and > 20 mU/ml FSH will be excluded. Enrollment will be available to all racial groups. Pregnancy will be excluded by measuring urinary hCG (human chorionic gonadotropins) by standard clinical testing procedure.

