 5. Subjects who satisfactorily complete above tasks including the 4 scheduled GCRC visits will have a pregnancy test and, if not pregnant, will be given a mammography, a bilateral breast MRI, and duplicate DEXA bone density tests (L2 to L4 and hip) during one of these GCRC visits. The mammogram results will be interpreted immediately as for all clinical mammography tests by a licensed radiologist. Dr. [name] (certified to interpret mammograms and breast MRI), our co-investigator will interpret the mammograms and if there are abnormalities, the subjects will be informed the test results by phone and by mail by the Radiology Staff according to the established clinical protocol in place in our Radiology Department. Specifically, the subjects will be advised to have additional diagnostic tests and be advised to consult their own physician for this follow-up. The cost of these follow-up diagnostic tests will not be the responsibility of this project. If the subjects have cancer lesions after further diagnostic tests, they will be excluded from the study. [name] will inform [name] and the PI of any abnormal test results. PI will also phone

- study subject, advise the subject to consult her personal physician, to have follow-up diagnostic tests, and to inform us the results of the diagnostic tests to determine their continuing eligibility in our study. [name] will also assess the density of these women according to the established diagnostic guideline. [name] who is certified to interpret DEXA results will interpret bone density results for this project.
6. Pregnancy test will be determined during screening and during pill intervention if menstrual cycle lengthens by 2 weeks or more, or within 48 hours prior to scheduled mammography and DEXA bone density tests.

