Lowering of female hormones due to prolonged soy isoflavone ingestion may lower bone density, which could increase the risk of eventually developing osteoporosis (thin bones) and bone fractures. But this is not a known risk. Soy isoflavones have been shown to improve bone mineral density in animals. Asian populations consuming high levels of soy have lower rates of hip fracture compared to western countries. Because the current available information does not allow us to estimate the benefit and the risk of soy consumption on bone density, observations about bone is a part of this study. The risk of osteoporosis might also be increased if subject's calcium intake is not sufficient during the study. Subjects will be advised to adjust their calcium intake if needed to maintain an adequate intake.

Potential adverse effects such as lengthening of the menstrual cycle and nipple fluid cytology will be looked for closely during this study. If menstrual cycle lengths increase by more than 2 weeks in 12% of the participants (e.g. 12 subjects) for more than 3 cycles, the pill assignment codes for these women will be examined to assess if this is intervention-related. If this is associated with treatment, the ovarian hormones of these subjects will be immediately analyzed. The luteal progesterone levels in these women should be less than 1 ng/ml. If cycle length increase persists in these women for longer than 3 months, breast density in these women will be assessed first by breast MRI (because this involves no radiation exposure) and is likely to show changes. The pill supplement will be terminated in these women, but will be continued in the remaining study subjects. If cycle lengths increase in more than 30% of participants and this increase is study related, the pill intervention will be terminated and end of study mammography, bone density test by DEXA, and breast MRI will be performed.

If women develop amenorrhea, transvaginal probe ultrasonography and endometrial biopsies will be performed to ensure no adverse effects on the uterus. [name]. (a co-investigator) will prescribe and perform these tests. Study subject will be provided with a written pathological report for consultation with subject's own primary physician. Reports will also be provided to the Medical Monitor.

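### The cycle-lengthening trigger for opening pill codes equates 12% of participants with 12 women, but in a 200-woman trial 12 is 6% and 12% is 24

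*Combined protocol and SAP*

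**What the plan says.** **Trigger.** The Risk and Benefit Assessment sets the condition for examining pill codes: "If menstrual cycle lengths increase by more than 2 weeks in 12% of the participants (e.g. 12 subjects) for more than 3 cycles". If the codes point to treatment, ovarian hormones in those women are assayed at once. If the lengthening persists beyond 3 months, breast density is assessed, first by MRI. Then: "The pill supplement will be terminated in these women, but will be continued in the remaining study subjects". A further rule in the same paragraph ends the pill intervention if lengthening affects more than 30% of participants and is study related.

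**Denominator.** The Abstract describes a study "with two arms, and 100 premenopausal women in each arm". Study Population says: "We expect to enroll the 200 subjects required for the study within 6-8 months". The amenorrhea rule, placed just before Statistical Analysis, reads: "If more than 6% of subjects (12 subjects) develop amenorrhea, we will break the code for these women". The power section adds: "We will recruit until 200 women complete at least 1.5 years of supplement".

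**Safety panel (secondary).** Clinical Procedures step 7 draws blood counts, chemistries, liver and thyroid tests, ferritin and lipids at every sixth cycle. The Risk and Benefit Assessment puts chemistries, liver and thyroid function, lipids and ferritin at three-month intervals. Experimental Design and Methods gives three-monthly safety monitoring in one place and, in another, chemistries, liver, thyroid and lipids at each outpatient visit.

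**The concern.** A safety threshold should give one number to count to. This one gives a percentage and a count that differ by a factor of two on the planned sample size. Someone working from the count would ask for the codes at 12 affected women; someone working from the percentage would wait for 24. The follow-up actions start at different times accordingly.

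Cycle lengthening of this kind heads the list of expected adverse events in the adverse-event reporting section, and safety is Aim #4, so the rule may well be needed. The laboratory panel serves the same aim: staff following the numbered procedures would take about half the panels that the risk section describes.

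**Working it through.** **1. The plan's own figures.** Inputs: 12% and 12 subjects (Risk and Benefit Assessment); 200 women, 100 per arm (Abstract, Study Population); 85 evaluable per arm, so 170 in all (power section).

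| Denominator | 12 as a percentage | 12% as a count |
|---|---|---|
| 200 planned | 12/200 = 6.0% | 0.12 × 200 = 24 |
| 170 evaluable | 12/170 = 7.1% | 0.12 × 170 = 20.4 |
| 100 (e.g. one arm) | 12/100 = 12% | 0.12 × 100 = 12 |

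The printed pair is exact only for a denominator of 100. The amenorrhea rule's pair is reproduced on 200: 0.06 × 200 = 12.

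**2. Could one arm be meant?** Codes are opened only after the trigger is met, so beforehand only the total across both arms is known. Twelve in one arm is possible once the total is 12 (split 12/0). It is certain only at 23, because 22 can split 11/11. A one-arm rule therefore gives no blinded count at which to act anywhere from 12 to 22.

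**3. If more than 200 are randomised.** The power section recruits until 200 women complete 1.5 years, and also expects 100 per arm to yield 85 evaluable. The first implies more than 200 randomised if anyone leaves early; the second implies 200. The stated attrition ("With an estimated attrition rate of 15% over the length of the study") covers two years, so I take loss by 1.5 years as an assumption between 0 and 15%:

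- randomised: 200 to 200/0.85 = 235
- 12% of these: 24 to 28.2
- 12 women as a share: 6.0% down to 12/235.3 = 5.1%

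The upper end probably overstates the number, since two-year loss is applied to a 1.5-year target. The text does not say whether the count or the percentage governs.

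**4. How much 12 versus 24 matters.** The documents give no event rates, so this is illustration only. With X ~ Binomial(200, p), where p is an assumed overall rate:

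| p | P(X ≥ 12) | P(X ≥ 24) |
|---|---|---|
| 3% | 2% | <0.1% |
| 6% | 54% | 0.1% |
| 9% | 95% | 9% |
| 12% | 99.8% | 53% |

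With separate arms of 100 and an assumed 10% on isoflavone, the chance of reaching 12 runs from 30% (placebo 0%) through 54% (placebo 2%) to 83% (placebo 5%). The chance of reaching 24 stays below 2% throughout.

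**5. The 30% rule.** It uses the same undefined word, participants: 0.30 × 200 = 60, against 0.30 × 100 = 30 if one arm were meant.

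**6. Safety panel.** Quarterly: 24/3 = 8 panels. Every 6 cycles, at an assumed 28 days: 730/168 = 4.3, so about 4. Cycle length cannot reconcile these: step 9 equates three cycles with one season, so six cycles is every second visit.

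**The case against.** **The parenthesis is only an example, and 100 is a natural denominator.** It could be one arm, or the first 100 women on pills. That is arithmetically possible, but the text states neither, and an example should still satisfy the percentage it illustrates. The one-arm version also cannot be applied blinded.

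**The only printed count is usable.** Twelve can be counted blinded and matches the count in the amenorrhea rule. This is a good reason to prefer 12. A reader might go further and infer that 12% is simply a slip for 6%. The documents do not support that: a looser limit for the milder event could be deliberate, and 24 remains possible.

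**Affected women are not left unwatched.** This stands. Clinical Procedures step 6 requires a pregnancy test "during pill intervention if menstrual cycle lengthens by 2 weeks or more", and step 15 has a similar test. Ultrasound and biopsy follow amenorrhea in any woman. Recurring adverse events go into aggregate reports that cover possible protocol modification or termination. It would be wrong to infer that no safety action occurs before the trigger.

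**Step 7 is an outlier, not one of two equal schedules.** This also stands. Three other statements favour quarterly or every-visit testing. One of them is loosely worded, since it also lists bone density, which is measured yearly elsewhere; the other two are specific to the blood tests.

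**The rate illustration has no documentary basis.** Agreed. It shows that the two readings can behave very differently, and no single figure in it should be relied on.

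**Conclusion.** The trigger is wrong as written. On the 200 women that the protocol plans, its percentage and count differ twofold, at 24 and 12. The protocol's own amenorrhea rule confirms that 12 corresponds to 6%. This conclusion needs no assumption beyond reading participants as all women in the study; the alternative reading that makes the figures agree is unstated and, per arm, unworkable under blinding. The documents do not show which figure was intended.

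The effect is confined to safety conduct: when codes are examined, hormones assayed, MRI done and pills stopped in affected women. A reader might infer that the whole-trial stopping rule is miscalculated as well. It is not, since it prints no count to contradict its 30%, but its denominator needs the same definition. Efficacy analyses do not change.

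The safety-panel discrepancy is real but lesser: one phrase in step 7 implies about 4 panels in two years, against about 8 elsewhere.

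**What to change.** In the Risk and Benefit Assessment, state the trigger on all randomised participants, with figures that agree and the medical monitor's confirmation:

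- *12 subjects (6% of 200)*, the cautious choice, or
- *12% of those randomised (24 of 200)*, if the higher limit is intended.

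Matching the amenorrhea threshold is optional. Add whether the count or the percentage governs if more than 200 are randomised, and apply the same denominator to the 30% stopping rule.

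In Clinical Procedures step 7, move the safety panel to each quarterly visit, where blood is already drawn.

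Cost: a line or two in the risk section and one phrase in step 7. The lower count may unblind affected women earlier. Quarterly panels add about 4 per woman over two years relative to step 7, and none relative to the risk section.

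### The cycle-lengthening trigger for examining pill codes equates 12% of participants with 12 subjects, but 12% of the planned 200 is 24

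*Combined protocol and SAP*

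**What the plan says.** The cycle-length rule is in the Risk and Benefit Assessment. Its trigger reads "If menstrual cycle lengths increase by more than 2 weeks in 12% of the participants (e.g. 12 subjects) for more than 3 cycles". Once it is met, "the pill assignment codes for these women will be examined to assess if this is intervention-related". If the lengthening is associated with treatment, the affected women's ovarian hormones are assayed at once. If it persists beyond 3 months, they have a breast MRI. The rule then says "The pill supplement will be terminated in these women, but will be continued in the remaining study subjects". A separate threshold in the same paragraph, more than 30% of participants, ends the intervention if the increase is study related.

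The Abstract plans a trial "with two arms, and 100 premenopausal women in each arm", and Study Population says "We expect to enroll the 200 subjects required for the study within 6-8 months". The amenorrhea rule, at the end of Experimental Design and Methods just before Statistical Analysis, reads "If more than 6% of subjects (12 subjects) develop amenorrhea, we will break the code for these women".

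The sample size section gives two other possible bases: "100 subjects per arm should provide 85 evaluable subjects at the completion of the study" and "We will recruit until 200 women complete at least 1.5 years of supplement".

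**The concern.** The trigger is written as a percentage with a count as its example, and the two differ by a factor of two against the planned total. The amenorrhea rule calls the same 12 women 6%.

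The trigger is the entry point to everything else in the rule: examining codes, urgent assays, the extra MRI and stopping pills. With 12 to 23 affected women, someone following the example would start these steps and someone following the percentage would wait. One risk is a late response to an adverse effect that the protocol says it will look for closely. The other is opening the codes of 6% to 11.5% of the women in a double-blind trial when the rule did not intend it.

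**Working it through.** **Inputs.** Trigger of 12%, with 12 subjects as the example (Risk and Benefit Assessment). Total of 200, with 100 per arm (Abstract; Study Population). Amenorrhea trigger of 6%, given as 12 subjects (Experimental Design and Methods). 85 evaluable per arm after 15% attrition, and recruitment until 200 complete 1.5 years (Power analysis and sample size justification).

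**Step 1: the plan's own equivalence.** Count = percentage × denominator. For amenorrhea, 0.06 × 200 = 12, which reproduces the stated figure with all 200 women as the base.

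**Step 2: the cycle-length rule on each available base.**

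| Base | 12% of base | 12 women as % of base |
|---|---|---|
| 200 planned | 24 | 6.0% |
| 170 evaluable (2 × 85) | 20.4 | 7.1% |
| about 235 randomised (200 / 0.85, if the 15% attrition applies by 1.5 years) | 28.2 | 5.1% |
| 100, one arm | 12 | 12.0% |

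No all-participant base gives 12. Only one arm does.

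**Step 3: the disputed zone.** With 200 women, and 12% read as 12% or more, the instructions conflict from 12 women (12/200 = 6%) to 23 women (23/200 = 11.5%).

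**Step 4: how likely the conflict is to arise.** Affected women accumulate during the trial, so a count that ends at 24 or more has first passed through 12 to 23. The relevant quantity is therefore P(at least 12), not the chance that the final count lies between 12 and 23. The documents give no incidence, so the rates below are assumptions. The total is the sum of Binomial(100, isoflavone rate) and Binomial(100, placebo rate).

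| Isoflavone v placebo | P(at least 12) |
|---|---|
| 4% v 0% | under 0.1% |
| 4% v 2% | 2% |
| 5% v 2% | 5% |
| 8% v 2% | 30% |
| 10% v 2% | 54% |
| 15% v 2% | 93% |
| 20% v 2% | 99.6% |

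At 20% v 2% the final count lies in 12 to 23 with probability 64%, which understates how often the conflict would be met.

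**Step 5: triggering with no drug effect.** Binomial(200, p), with the same assumed background rate in both arms.

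| Background rate | P(at least 12) | P(at least 24) |
|---|---|---|
| 2% | 0.08% | under 0.01% |
| 3% | 1.8% | under 0.01% |
| 4% | 11% | under 0.01% |
| 5% | 30% | under 0.01% |

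**The case against.** **The count may be per arm.** Twelve of 100 fits both figures exactly, and it may be what was meant. But the sentence refers to participants and names no arm, and the codes are examined only after the trigger is met, to find out whether the lengthening is related to the intervention. It would go too far to say that nobody could count by arm: subjects, research staff and investigators are blinded, but the available text does not say who holds the treatment code. What stands is that a per-arm rule would have to be stated, together with who applies it.

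**The percentage is the rule and the count only an illustration.** This is reasonable. Read so, the thresholds form a graded scheme: 6% for amenorrhea, 12% for cycle lengthening, more than 30% for ending the intervention. It favours correcting the example rather than the percentage. It does not remove the conflict, because no stated total of participants makes 12 women 12%.

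**Other safeguards do not depend on the trigger.** This also stands. A pregnancy test follows lengthening of 2 weeks or more (Clinical Procedures, step 6). Luteal blood is drawn four times a year (step 7). Ultrasound and biopsy follow amenorrhea (Risk and Benefit Assessment). Evaluation of prolonged or absent menses is free of charge (Cost of Participation). A reader might infer that women with 12 to 23 cases among them would go without care; these provisions show otherwise.

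**Low incidence may make the conflict academic.** The Introduction reports no adverse reproductive effects in the earlier feeding studies. Those were small and short, so they point to low rates without establishing them.

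**Conclusion.** The trigger is inconsistent as written, by a factor of two: 24 women by the percentage, 12 by the example. That conclusion needs only the planned total of 200 and the amenorrhea rule's own arithmetic. The probability that the conflict arises rests on assumed rates, from under 0.1% to over 99% across those shown. It would rarely matter at isoflavone rates near 4% and would nearly always matter near 20%.

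Three stronger conclusions are not supported. The documents do not show which of the two figures is the error; agreement of the count with the amenorrhea rule does not prove that 6% was intended. They do not show that the conflict occurred in this trial. And the trigger does not enter the sample size or the primary analysis of breast density. The effect is on safety monitoring and blinding, and the point is minor.

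**What to change.** State one trigger, as a pooled, blinded count with one denominator. The least invasive form keeps the percentage and corrects the example: *12% of the participants (24 of the planned 200, both arms combined)*.

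If the sponsor meant 12 women, write: *at least 12 women, both arms combined (6% of the planned 200)*. The wording should be at least 12, not more than 12, because the present example triggers at 12. Fixing the base at the planned 200 keeps percentage and count in step even if more than 200 are randomised. The price of this lower trigger is more unblinding without a drug effect: about 11% and 30% at assumed background rates of 4% and 5%, against under 0.01% for a trigger of 24. If one arm was meant, say so, and say who counts by arm.

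The cost is one sentence in an amendment and no new data, since cycle day 1 is already recorded throughout. Post-intervention follow-up describes pill-taking in the past tense. If it has ended, the report should state which trigger was applied and how many women met it.

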Reporting of Serious and Unexpected Adverse Events:

Adverse experiences that are both serious and unexpected will be immediately reported by telephone within 24 hr and in writing within 3 days to: 1) UTMB IRB, 2) UTMB GCRC, and 3) UTMB Research Subject Advocate.

A UTMB IRB Adverse Event Report form will be used to report individual serious adverse event. For recurring adverse event, an aggregate report form will be generated to provide summary statistics for the study that will include resolution and potential protocol modification or study termination. The adverse event reports will include the name of P.I. ([name].) and co-investigators ([name]., [name]., and [name].), name of the study (Mammographic Density and Soy Isoflavones), UTMB IRB number (03-260) and UTMB GCRC protocol number (#635), the number of subjects enrolled to date, the number and type of serious and unexpected adverse events previously reported. The report of the medical monitor ([name]) and a follow-up report describing the resolution of the adverse event will also be provided.

The expected adverse events are lengthening of menstrual cycle by more than 2 weeks per cycle in the absence of pregnancy for more than 3 cycles, amenorrhea, unexpected vaginal bleeding, breast lumps, abnormal endometrial histology/cytology, abnormal nipple aspirate cytology, and abnormal blood chemistries. Unanticipated adverse events are breast cancer, ovarian cancer, uterine cancer, intercurrent illness and intercurrent injuries. Serious adverse events are life threatening drug interaction, death, breach of confidentiality, and hospital admission.

Disposition of Data: All notebooks, Harvard DAQ, data collection forms, signed copies of the informed consent, and PHQF relating to this study will be kept in the locked filing cabinets on the [name], Division of Human Nutrition, Department of Preventive Medicine and Community Health, [name] where PI's office is located. The electronic data will be stored on the UTMB PMCH server (pmch on utmbf4) and the Bioinformatics Core facility of GCRC until published, and then archived in CD ROMs at the end of the study. The records will be kept for at least five years after the completion of publications resulting from this support.

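### The cycle-lengthening threshold for examining the treatment codes gives a percentage and a count that disagree for 200 women: 12% is 24, and 12 women are 6%

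*Combined protocol and SAP*

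**What the plan says.** The Risk and Benefit Assessment section has a two-step rule for lengthening of the menstrual cycle.

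- **First step.** "If menstrual cycle lengths increase by more than 2 weeks in 12% of the participants (e.g. 12 subjects) for more than 3 cycles", the codes of the affected women are examined to see whether the change is due to the intervention. If it is associated with treatment, their ovarian hormones are analysed at once. If it persists beyond three months, breast density is assessed in these women. Their pills are stopped while the other women continue.
- **Second step.** "If cycle lengths increase in more than 30% of participants and this increase is study related, the pill intervention will be terminated". No count is printed for this step.

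The Abstract gives 100 women in each of two arms. Study Population says: "We expect to enroll the 200 subjects required for the study within 6-8 months". The power section adds: "We will recruit until 200 women complete at least 1.5 years of supplement".

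A separate rule for amenorrhea stands at the end of Experimental Design and Methods: "If more than 6% of subjects (12 subjects) develop amenorrhea, we will break the code for these women". It continues: "If amenorrhea is related to soy isoflavone treatment, the study will be terminated".

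Experimental Design and Methods also states that subjects, staff and investigators are blinded to assignment.

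**The concern.** The first step is a safety threshold that someone has to apply during the trial. Its percentage and its count cannot both be right for the planned number of women. One person could ask for the codes at the twelfth affected woman, and another could wait for the twenty-fourth. Both would be following the text.

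What is at stake is when a treatment-related effect on the cycle is first examined, and so when hormone analysis and stopping of pills in affected women can begin. The comparison of the arms at the end of the study does not depend on this threshold.

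**Working it through.** **Inputs from the protocol.** 200 women, 100 per arm (Abstract, Study Population). Expected attrition 15%, leaving 85 per arm (power section). Cycle-lengthening threshold 12%, illustrated as 12 women (Risk and Benefit Assessment). Amenorrhea threshold 6%, given as 12 women (Experimental Design and Methods).

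**Step 1: reproduce the printed count as percentage × base.**

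| Rule | Base | Result | Printed count | Agrees? |
|---|---|---|---|---|
| Amenorrhea, 6% | 200 planned | 0.06 × 200 = 12 | 12 | yes |
| Cycle lengthening, 12% | 200 planned | 0.12 × 200 = 24 | 12 | no |
| Cycle lengthening, 12% | 170 evaluable (2 × 85) | 0.12 × 170 = 20.4 | 12 | no |
| Cycle lengthening, 12% | 100, one arm | 0.12 × 100 = 12 | 12 | yes, but the text says participants |

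The amenorrhea rule reproduces on 200. The cycle-lengthening rule does not: 12/200 = 6%.

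**Step 2: how much the reading matters.** Let X be the number of women meeting the cycle criterion over two years. X is the sum of Bin(100, p) on isoflavone and Bin(100, q) on placebo. The two readings are X ≥ 12 and X ≥ 24. The rates are assumptions, and dropout is ignored.

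| Isoflavone p | Placebo q | P(X ≥ 12) | P(X ≥ 24) |
|---|---|---|---|
| 15% | 0% | 0.84 | 0.01 |
| 15% | 3% | 0.96 | 0.09 |
| 20% | 0% | 0.99 | 0.19 |

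**Step 3: the price of the lower trigger.** With the same rate in both arms (no treatment effect), X is Bin(200, rate).

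| Rate in both arms | P(X ≥ 12) | P(X ≥ 24) |
|---|---|---|
| 2% | 0.001 | <0.001 |
| 3% | 0.018 | <0.001 |
| 4% | 0.11 | <0.001 |
| 5% | 0.30 | <0.001 |
| 6% | 0.54 | 0.001 |

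A trigger at 12 is seldom reached by background events alone up to about 3%. It is reached fairly often from 5% upward.

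**Step 4: the 30% step.** 0.30 × 200 = 60, so on its face the step means more than 60 women. No conflicting count is printed.

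**The case against.** The best defence is that the count is only introduced as an example, and that 12 is exactly 12% of one arm of 100. Crossing the threshold does not stop the trial; it opens the codes of affected women. Individual protection does not wait for it either. Women with amenorrhea have ultrasound and biopsy, with results passed on ("Reports will also be provided to the Medical Monitor"), and the adverse event section provides that "For recurring adverse event, an aggregate report form will be generated to provide summary statistics for the study".

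Most of this stands as a limit on the consequences, but it does not settle the threshold. An example should illustrate the rule, and this one contradicts it on the only base the sentence names. A one-arm count cannot be kept by blinded staff. The individual work-up and the aggregate reports do not say when the codes are to be examined.

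Two stronger readings are tempting, and the documents do not support them.

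- **The 30% step as equally ambiguous (30 or 60 women).** It prints no count and refers to participants, so it means more than 60 of 200. A base of 100 would have to be carried over from the faulty example.
- **The amenorrhea rule as unable to tell a treatment excess from background, because it pools the arms.** The pooled count is only a gate. Once it is passed, the code is broken for the affected women, and termination depends on whether the amenorrhea is related to isoflavone. With equal allocation the unblinded split is informative: 11 v 2 gives a two-sided Fisher p of 0.018. Keeping the blind until a preset total is a defensible choice. The rule gives no criterion for relatedness, and it leaves open whether action comes at 12 or above 12. These are minor clarifications.

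**Conclusion.** The point holds for the first step of the cycle-lengthening rule. As written, the threshold is wrong for 200 women and can be applied at 12 or at 24. The difference is large for plausible uses of the rule: about 0.84 against 0.01 at an assumed 15% v 0%.

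The arithmetic conflict rests only on the planned sample size and needs no assumption. The probabilities rest on assumed two-year rates, 100 women per arm, independent events and no dropout; the documents give no background or treatment rate for persistent cycle lengthening. The correction should be made because this is a safety threshold, but it is a correction of wording. It does not show that the amenorrhea rule or the 30% step is in error, or that the final safety comparison is compromised.

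**What to change.** - **Make the two figures agree.** The preferred form is 6% of participants (12 of 200). It is the earlier and safer trigger and matches the equivalence already used for amenorrhea. If 12% is truly intended, print 24.
- **State the denominator** as all women randomised. Recruitment continues until 200 complete 1.5 years, so more than 200 may be randomised; say whether the count or the percentage then governs.
- **Print the 30% step as a count on the same base:** more than 60 of 200.

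The cost is a few words and an amendment, with no added patients, visits or procedures. The downside of the lower trigger is a greater chance that background events alone lead to an early look at the codes: about 0.02 at a 3% rate in both arms, 0.30 at 5%. That look does not itself stop the trial.

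A table of events by arm, prepared for the medical monitor alone, is optional. Its benefit depends on the background rate. With an example prompt (isoflavone higher, nominal Fisher p < 0.05 at any of eight looks), a 10% v 3% amenorrhea difference would be flagged with probability 0.49. The existing gate, read as above 12, is passed with probability 0.54.
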